6.4. Statistical Methods

6.4.1 Statistical Methods for Efficacy Analyses

6.4.1.1 Primary Endpoints

AUC-ROCs for 1-year, 3-year, 5-year of recurrence and mortality will be estimated for each reader in **each review condition** (aided or unaided, and the difference between them) based on the reader's interpretations of all cases. The account for right-censor data, the inverse probability of censoring weighting estimate was used for the cumulative/dynamic time-dependent ROC curve approach by Blanche et al. [15].

AUC-ROCs between reading conditions will be compared using the standard MRMC analysis of variance (ANOVA) method of Obuchowski and Rockette (OR), where both reader and case are random effects, to ensure generalization of the study results to both the population of readers and the population of cases.

The average AUCs within each reading condition, as well as its standard error and two-sided 95% confidence intervals (CIs) will be reported. The average difference in AUCs, its standard error, corresponding two-sided 95% CIs, and statistical inference will be computed, referencing to the approach in Obuchowski and Rockette. No adjustments for covariates are planned.

Sensitivity analysis may be conducted using OR approach with only reader (sensitivity analysis 1) and only case (sensitivity analysis 2) as random effects.

6.4.1.2 Secondary Endpoints

Analyses of sensitivity and specificity will also use standard MRMC ANOVA methods to compare reader performance under different reading condition and use two-sided 95% CIs to quantify uncertainty. Sensitivity and specificity each provide additional information needed to understand the expected impact of using the prediction tool on clinical practice. Their analysis and reporting, including confidence intervals, is thus required to provide a complete description of reader performance.

Analysis of Inter-rater reliability or other ordinal outcomes collected under different reading condition will use generalized linear mixed model (for appropriate link function) with reading condition as a covariate and both reader and case are random effects.

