6.2.3 Exploratory Endpoints

Inter-rater reliability: the consistency of ratings made by readers on the cases

Objective: To evaluate aided versus unaided with respect to inter-rater reliability for readers' recommendation on initiating surgical treatment; To evaluate aided versus unaided with respect to inter-rater reliability for readers' recommendation on the timing of the first post-surgery follow-up.

Decision-making confidence: confidence of a reader in completing the evaluation for a case

Objective: To evaluate aided versus unaided with respect to (improve) decision-making confidence in predicting the disease progression and making recommendation for a case. The general confidence on prediction model in pre and post study will also be evaluated.

Decision-making time: duration of a reader in completing the evaluation for a case

Objective: To evaluate aided versus unaided with respect to (reduced) decision-making time in completing a case evaluation.

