6.6 Multiplicity

The study allocated two-sided $\alpha = 0.05$ to test AUC for 3-year mortality between reading conditions. All the other analyses are exploratory in nature. No multiplicity adjustment will be implemented. The nominal p-value will be reported.

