6.7. Sample Size and Power Calculation

This study is well powered for the primary endpoint AUC of 3-year mortality prediction. A sample size of 166 cases and 12 readers was selected for this study. The method of Obuchowski[14] is used to determine the number of readers required in a fully crossed design to provide at least 80% power to detect a 0.05 absolute advantage in AUC for reading, at statistical significance level $\alpha = 0.05$ (two-sided). The disease cases to non-disease cases (for 3-year mortality) will be randomly selected with an approximately 1:1 ratio from the patient dataset pool, which is independent from the dataset used to training the prediction tool. A balanced disease vs non-disease design may not reflect the actual disease prevalence in the real-world setting but enhance statistical efficiency in assessing the accuracy of diagnostic tests. The sample size calculations conservatively assume that both readers and cases are random effects.

Due to this being a pilot study, there were no estimate of variance components. Variance component estimates (via Obuchowski and Rockette approach using jackknife method) from previous MRMC studies that use a similar study design as the proposed (regardless of the original endpoint types) were leveraged in the power and sample size calculation of this study. All power estimates are dependent upon the appropriateness of the assumed variance components.

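### The mixed model for ordinal outcomes names random effects for reader and case only, so if readers respond differently to the tool, its nominal aided-versus-unaided intervals can be far too narrow

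*Protocol*

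**What the plan says.** Protocol section 6.4.1.2 covers "Analysis of Inter-rater reliability or other ordinal outcomes collected under different reading condition" and prescribes a "generalized linear mixed model (for appropriate link function) with reading condition as a covariate and both reader and case are random effects". It names no interaction between condition and either reader or case. It does not use the term intercepts only, but two crossed random intercepts is the plain reading.

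The same section analyses sensitivity and specificity by MRMC ANOVA. Section 6.4.1.1 compares AUCs by the Obuchowski-Rockette method with reader and case both random, "to ensure generalization of the study results to both the population of readers and the population of cases".

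The listed outcome that most clearly asks for an aided-versus-unaided shift and could be ordinal is exploratory. It is defined as "confidence of a reader in completing the evaluation for a case", and section 6.2.3 compares the conditions "with respect to (improve) decision-making confidence in predicting the disease progression and making recommendation for a case". On everything outside the primary test, section 6.6 says: "The nominal p-value will be reported".

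**The concern.** A random intercept for reader lets readers differ in overall level. It does not let them differ in how far the tool moves them, and the same holds for cases. Without such terms, the 12 x 166 x 2 = 3,984 readings count, given the intercepts, as independent replicates of the condition effect. If readers do respond differently, the effective number of units for that part of the error is 12.

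The protocol itself gives reasons to expect such differences. Section 4.1 recruits four junior, four mid-level and four senior physicians. Section 6.8 plans to examine whether the benefit is consistent across expertise levels. Section 6.4.3 treats confidence in the tool as a baseline reader characteristic. Section 5.2 shows every reader the same case-specific predictions, which is a source of case-by-condition variation.

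The Obuchowski-Rockette method carries reader-by-condition variation by construction. Calling reader and case random in a mixed model does not bring it in. At stake is whether a nominal p-value or interval for a change in confidence describes physicians in general or only these 12.

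**Working it through.** **No figure to reproduce.** The protocol gives no number for this model. Its one design figure (at least 80% power for a 0.05 AUC difference) concerns the primary analysis, and section 6.7 states that no variance-component estimates were available. The variance inputs below are therefore assumptions, shown over a range.

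**Inputs from the protocol.** "A sample size of 166 cases and 12 readers was selected for this study" (section 6.7). Every reader reads every case in both conditions (section 6.3), which gives 12 x 166 = 1,992 pairs and 3,984 readings. The risk score has four categories (section 3.2). The confidence scale is not visible.

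**Check 1: closed form, log-odds scale.** Let τ be the SD across readers of the aided-minus-unaided log-odds shift. With four equally likely categories:

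- SE of the model as written: √[12 / (3984 × (1 − 4 × 0.25³))] = √(12 / 3735) = 0.0567
- True SE: √(0.0567² + τ²/12)
- False-positive rate: 2 × [1 − Φ(1.96 × 0.0567 / true SE)]

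| τ | True SE | Ratio to 0.0567 | False positives at nominal 5% |
|---|---|---|---|
| 0.2 | 0.081 | 1.43 | 17% |
| 0.3 | 0.104 | 1.83 | 28% |
| 0.5 | 0.155 | 2.74 | 47% |

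Five categories instead of four change 0.057 only to 0.056.

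**Check 2: proportional-odds fits to null data.** Five levels, case-specific shift SD 0.3, 220 data sets per setting. At τ = 0.2 / 0.3 / 0.5 the reported SE stayed at 0.057, while the estimates had an SD of 0.077 / 0.096 / 0.157. False positives were 14% / 30% / 47%. A separate run of 120 data sets gave 15% / 21% / 52%. With 220 data sets the Monte Carlo margin is about 6 points. With interaction SDs of zero the rate was 4%.

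**Check 3: when is the model too narrow, and when too wide?** Take a balanced linear analogue with variances RT (reader-by-condition), CT (case-by-condition), RC (reader-by-case) and residual e = 1. On this scale τ² = 2RT.

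- True variance of the difference: 2(RT/12 + CT/166 + e/1992)
- Variance from the model as written: 2s²/1992, where s² = [11(e + 166RT) + 165(e + 12CT) + 1815(e + 2RC) + 1815e] / 3806

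| RT | CT | RC | True SE / reported SE | False positives |
|---|---|---|---|---|
| 0 | 0 | 0 | 1.00 | 5.0% |
| 0 | 0 | 0.3 | 0.88 | 2.6% |
| 0.002 | 0 | 0.3 | 1.02 | 5.4% |
| 0.01 | 0 | 0.3 | 1.44 | 17.2% |
| 0.05 | 0.05 | 0.3 | 2.72 | 47.1% |
| 0 | 0.05 | 0.3 | 1.10 | 7.6% |

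Equating the two variances puts the break-even at about 165RT + 11CT = RC. Intervals are too narrow above it and too wide below it. With RC = 1 and CT = 0, that is RT of about 0.006, or τ = √(2 × 0.006) = 0.11.

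**Check 4: ordinal simulation with large reader-by-case variance.** Four levels, logistic latent scale, RC = 1, 4,000 null data sets per setting. Category scores were analysed by additive ANOVA as a stand-in for the mixed model, so the percentages are illustrative.

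| RT | CT | τ | As written | With both condition interactions, Satterthwaite df |
|---|---|---|---|---|
| 0 | 0 | 0 | 2.3% | 4.2% |
| 0.01 | 0 | 0.14 | 7.2% | 5.2% |
| 0.05 | 0 | 0.32 | 21.8% | 5.3% |
| 0.1 | 0.1 | 0.45 | 36.9% | 5.6% |
| 0 | 0.1 | 0 | 5.6% | 5.3% |
| 0 | 0.25 | 0 | 8.7% | 4.7% |

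Across all nine settings run, the corrected analysis stayed between 4.2% and 5.6%. Nearly all the inflation comes from reader-by-condition variation; case-by-condition variation alone does little.

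**The case against.** The strongest reply is that section 6.4.1.2 is silent on interactions and does not exclude them, and that link function, random-effects structure and degrees of freedom are normally settled in an SAP, which is not shown. This stands in part: an SAP may already contain the fuller structure. But the section does name the covariate and the random effects, and a statistician who followed it literally would fit the two-intercept model. It is a stated model, not an omitted detail.

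A second reply is that the direction of the error is not established. This stands. Someone might infer that the intervals must be too narrow. The protocol gives no variance components that would support this, and with reader-by-case variance and no condition interaction the intervals are slightly too wide.

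A third reply concerns reach, and it also stands. Someone might infer that claims about changed follow-up timing, changed risk ratings or decision time rest on this model. Section 6.2.3 frames the timing endpoint as "inter-rater reliability for readers' recommendation on the timing of the first post-surgery follow-up", which is agreement and not a shift, and section 6.2.2 does the same for risk ratings. Decision time is a duration and falls outside the ordinal sentence. Confidence itself is covered only if its scale is ordinal.

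Finally, section 1.5 limits hypothesis testing to the primary endpoint, and the sentence on generalizing to readers and cases is written for the AUC comparison. No confirmatory conclusion is at risk. Exploratory status does remove the need for multiplicity control, but it does not make an interval with poor coverage informative.

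**Conclusion.** The point holds conditionally. Fitted as written, the model gives correct or slightly conservative inference only if readers respond almost identically to the tool. At reader-specific log-odds shift SDs of 0.2 to 0.5, the nominal 5% test runs at roughly 15% to 50%. Large reader-by-case variance lowers these rates somewhat (21.8% at an SD of 0.32). The SDs are assumptions. The mixed experience levels and the planned expertise subgroups make differences in response plausible, but nothing in the protocol measures them.

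The consequence is limited to nominal, exploratory inference on ordinal shifts, chiefly confidence. It would be wrong to infer that the trial's main result is affected: the AUC, sensitivity and specificity comparisons use MRMC methods. The change is worth making because it is cheap and brings the ordinal outcomes into line with those analyses.

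**What to change.** In section 6.4.1.2, replace the random-effects clause for ordinal outcomes with: *random effects for reader, case, reader-by-condition and case-by-condition (and reader-by-case if estimable), with a small-sample degrees-of-freedom method, such as Satterthwaite or an equivalent reader-level reference, for the condition effect*. If an SAP already specifies this, a cross-reference is enough. Limit the change to the ordinal outcomes that the section covers.

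A fixed 11 degrees of freedom need not be imposed: with both interactions added it gave 1% to 4% false positives in the proportional-odds runs, which is conservative.

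The cost is one sentence and standard mixed-model software. Intervals will be wider, and convergence has to be checked with only 12 readers.

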3.2. Rationale for Endpoints

Primary endpoints:

The Area Under the Receiver Operating Characteristic Curve (AUC-ROC) for predicting post-operative 3-year mortality, comparing clinician performance with and without the aid of the prediction model according to risk scores: (low risk) $<10\%$, 2 (Moderate Risk) $10\%-30\%$, 3 (High Risk) $30\%-70\%$ and 4 (Critical Risk) $>70\%$.

Secondary endpoints:

The AUC-ROC for predicting post-operative 1-year recurrence, 3-year recurrence, 5-year recurrence, 1-year mortality, and 5-year mortality, comparing clinician performance with and without the aid of the prediction model according to risk scores: (low risk) $<10\%$, 2 (Moderate Risk) $10\%-30\%$, 3 (High Risk) $30\%-70\%$ and 4 (Critical Risk) $>70\%$.

After surgery, all patients were routinely monitored for recurrence through thoracic, abdominal, and pelvic computed tomography, magnetic resonance imaging of the liver, and serum carcinoembryonic antigen (CEA) measurements. The first postoperative assessment took place one month post-surgery, and subsequent evaluations were conducted in the outpatient clinic every three months. The rates of recurrence or mortality at one year, three years, and five years post-operation were determined based on these earlier follow-up reviews.

4. Sample Population

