5.2. Reading Procedure

The standardized training will be provided to all readers how to use medical record system to get patients data, and how to complete the questionnaire. Reading will be conducted in a blinded fashion in the sense that the readers will not have access to the identification information and post-operative recurrence and modality status during either the aided or unaided portion of the reading. During the reading process, whether aided or unaided, the readers will only have access to anonymous medical information relevant to surgery, as well as information pertaining to the period prior to the surgical procedure. This includes medical records, demographics, imaging examinations, preoperative biochemical markers, surgery-related variables, tumor pathological characteristics, genetic markers, and treatment information from the medical records system. In the aided session, the individualized predicated KM curves and landmark survival probabilities based on prediction models for the case will be presented in addition to the information provided in unaided session.

Each reader will be asked to complete a questionnaire about the risk score of post-operative 1-year, 3-year, and 5-year recurrence or mortality, their confidence of the making the decision and the recommended timing for the first follow-up examination after surgery. Time from starting to read the medical history to completing the questionnaire will be recorded.

Patient cases will be equally and randomly split between Dataset A and Dataset B. The readers are also equally and randomly split between Group A and Group B. During each session each reader reads all the cases assigned to the group they belong to in that session. There will be at least a one-month washout period between sessions.

Study Schema like below

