6.3. Randomization/Treatment Assignment

This is a retrospective MRMC study, which employs a fully crossed design in which all cases will be evaluated the same way by all study readers, such that there are no treatment assignments or treatment groups.

The 12 readers will be randomly allocated into two groups, reader group A and B. The 166 cases will be randomly allocated into two subsets of 83 cases each, case subsets A and B. The cases within a case subset will be assigned to each reader in a randomized case order. Each reader will read one case subset with prediction tool aided and another case subset as unaided during Session 1, and the complementary unaided and aided during Session 2.

Study case identification numbers and study reader numbers will be assigned to all cases and readers and used to protect their identities in statistical analysis and in reporting of results.

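### The mixed model for ordinal outcomes names only reader and case random effects, so the standard error of the aided-unaided difference can be wrong in either direction

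*Protocol*

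**What the plan says.** Protocol section 6.4.1.2 sets the model and its scope: "Analysis of Inter-rater reliability or other ordinal outcomes collected under different reading condition will use generalized linear mixed model", "with reading condition as a covariate and both reader and case are random effects". No interaction between reader, case and condition is named.

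Section 6.3 sets the layout: "Each reader will read one case subset with prediction tool aided and another case subset as unaided during Session 1", with the two roles exchanged in Session 2. Sections 3.1 and 6.3 call the design fully crossed. Section 6.7 gives the numbers: "A sample size of 166 cases and 12 readers was selected for this study".

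Two other places bear on whether the tool's effect may vary. In the aided session, section 5.2 says that "the individualized predicated KM curves and landmark survival probabilities based on prediction models for the case will be presented". Section 6.8 plans to look at the benefit separately for junior, mid-level and senior physicians.

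Sections 1.5 and 6.6 reserve hypothesis testing for the 3-year mortality AUC. Everything else is exploratory, with nominal p-values.

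**The concern.** A crossed reader study in two conditions has three two-way interactions, and the sentence in 6.4.1.2 names none of them.

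- **Reader-by-case.** A reader who is unusually pessimistic or confident about one case will tend to be so in both sessions. This component cancels in the aided-unaided difference. A model without it leaves it in the residual, which inflates the standard error.
- **Reader-by-condition.** Some readers may respond to the tool more than others. This does not cancel, and it averages over only 12 readers. A model without it spreads it over 3,984 ratings as if it were independent noise.
- **Case-by-condition.** The tool shows case-specific output, so it may move ratings up for some cases and down for others. This does not cancel either, and it averages over 166 cases.

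The first omission costs power and the other two produce false positives. If the model is run as written, neither the coverage of the nominal 95% intervals nor the size of the nominal p-values is assured for ordinal level comparisons.

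**Working it through.** **Inputs.** Readers J = 12 and cases K = 166 (6.7); two conditions, fully crossed (6.3); a four-category risk scale (3.2). Section 6.7 says that no variance-component estimates were available for this study and prints none, so all components below are assumptions.

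**The plan's own figure.** The only sizing figure is 80% power for an AUC difference of 0.05. By the normal formula it implies a standard error of 0.05 / (1.960 + 0.842) = 0.0178. It cannot be reproduced without the components, and it concerns the primary endpoint, so nothing here rests on it. No figure is given for the mixed model.

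**Step 1: pairs.** 12 × 166 = 1,992 pairs, or 3,984 ratings.

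**Step 2: closed form (linear analogue, residual variance 1).** Let RC, TR and TC be the reader-by-case, reader-by-condition and case-by-condition variances.

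- True variance of the mean difference: 2·TR/12 + 2·TC/166 + 2/1992 = (2/1992)·(1 + 166·TR + 12·TC).
- Variance reported by a model with reader and case intercepts only: (2/1992)·MS, where MS = [1815·(1 + 2·RC) + 11·(1 + 166·TR) + 165·(1 + 12·TC) + 1815] / 3806.
- Ratio of model SE to true SE: √[MS / (1 + 166·TR + 12·TC)].

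*Reader-by-case only.* RC = 1: MS = (5445 + 11 + 165 + 1815)/3806 = 1.954, ratio √1.954 = 1.40. For RC = 0.25, 0.5 and 2 the ratios are 1.11, 1.22 and 1.71.

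*RC = 1 with by-condition variation.*
- TR = 0.01: MS = 7454.26/3806 = 1.959; true term 1 + 1.66 = 2.66; ratio √(1.959/2.66) = 0.86.
- TC = 0.10: MS = 7634/3806 = 2.006; true term 1 + 1.2 = 2.2; ratio 0.95.
- TR = 0.02 with TC = 0.10: ratio 0.60.

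*Break-even at RC = 1.* The two errors cancel at TR = 0.0058 or TC = 0.083. The first is a between-reader SD in the aided-unaided difference of √(2 × 0.0058) = 0.11 residual SDs.

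**Step 3: adding reader-by-case alone.** The RC line then leaves the residual: MS = [11·(1 + 166·TR) + 165·(1 + 12·TC) + 1815] / 1991.
- TR = 0.01: MS = 2009.26/1991 = 1.009; ratio √(1.009/2.66) = 0.62, worse than 0.86.
- TC = 0.10: MS = 2189/1991 = 1.099; ratio √(1.099/2.2) = 0.71, worse than 0.95.

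**Step 4: ordinal simulation.** Four-category cumulative-logit data with no true condition effect; reader SD 0.6 and case SD 1.2 on the logit scale; 500 runs per scenario; the model fitted with reader and case intercepts only.

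| RC | TR | TC | Model SE / true SE | Type I error at nominal 5% |
|---|---|---|---|---|
| 0 | 0 | 0 | 1.01 | 4.0% |
| 1.1 | 0 | 0 | 1.14 | 2.8% |
| 3.3 | 0 | 0 | 1.37 | 0.6% |
| 3.3 | 0.05 | 0 | 0.79 | 12.2% |
| 3.3 | 0 | 0.5 | 0.89 | 8.6% |
| 3.3 | 0.05 | 0.5 | 0.67 | 20.2% |
| 1.1 | 0.1 | 0.5 | 0.45 | 38.4% |

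A separate simulation with reader SD 0.8 gave similar ratios for reader-by-case persistence alone: 0.059/0.055 = 1.07, 0.059/0.051 = 1.16 and 0.058/0.041 = 1.41 at latent within-pair correlations of 0.10, 0.25 and 0.5.

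**The case against.** **The wording is shorthand.** Section 6.4.1.2 does not say that reader and case are the only random effects. Nearly the same phrase describes the Obuchowski-Rockette method in 6.4.1.1, where the covariances between conditions come with the method. A separate SAP, not available for this point, may list the interactions. This stands in part. In 6.4.1.1 a named method supplies the missing structure, whereas a generalized linear mixed model has only the random effects it is given. The protocol names two, and that set does not fit the crossed design.

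**A one-directional reading is tempting.** A reader might infer that the model treats the ratings as unpaired, so that its intervals are simply too wide and real effects are missed. The documents do not support this. The two ratings share the reader and case intercepts, which cancel in the difference; only the reader-by-case part of the pairing is lost. The same sentence also leaves out by-condition variation, which acts the other way. Such variation is plausible here: the tool's output is case-specific, and shifting every rating equally would leave the AUC unchanged, so the benefit the trial hopes for implies effects that differ between cases.

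**Materiality is low.** This stands. These analyses are exploratory, and for risk ratings and follow-up timing the listed rating-level endpoint is reliability, not a shift in level. Decision-making confidence is the clearest outcome affected. The questionnaire is not shown, so its being recorded on an ordinal scale is itself an assumption.

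**Conclusion.** The point holds as a two-way error. Followed literally, the model in 6.4.1.2 gives a standard error for the aided-unaided difference that is about 1.1 to 1.4 times too wide in the ordinal simulations if reader-by-case persistence is the only omitted component. It becomes too narrow once modest by-condition variation is present (ratios of 0.89 down to 0.45 in the scenarios tried). Which error dominates cannot be settled from the protocol. All sizes rest on assumed variances; with no interactions at all, the model is correct (ratio 1.01).

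Two limits apply. The primary AUC comparison uses a different method and is not affected. Comparing inter-rater reliability between conditions is also outside this point: the condition coefficient measures a shift in rating level, and adding random effects does not turn it into a comparison of agreement. The matter is minor, but worth correcting because nominal p-values will be reported.

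**What to change.** In section 6.4.1.2, or in the SAP, state *random effects for reader, case, reader-by-case, reader-by-condition and case-by-condition*. The terms should go in together: reader-by-case should not be added alone, because Step 3 shows that this can worsen the error.

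If the ordinal model does not converge, analyse the within-pair difference in rating (aided minus unaided) with reader and case as crossed random effects. Reader-by-case cancels in that difference, and the two random effects carry the by-condition variation, so its variance has the form of the true variance in Step 2. The price is that category codes are treated as equally spaced and the result is a mean difference in score, not an odds ratio.

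The cost is one phrase and a heavier fit, with 1,992 pair-level effects and possible convergence problems. No new data, readers or cases are needed.
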